# **1. INTRODUCTION**

# 1.1. Mechanism of Action/Indication

Lorlatinib is a third-generation, oral, reversible, ATP-competitive, macrocyclic TKI of ALK and ROS1. Compared with second-generation inhibitors, lorlatinib was specifically designed to penetrate the CNS and to overcome known secondary resistance mutations in the ALK tyrosine kinase domain.

# 1.2. Background and Rationale

Lung cancers that harbor chromosomal rearrangements of ALK constitute about 3-5% of NSCLCs and are highly responsive to small-molecule TKIs that target ALK. Standard treatment of patients with advanced ALK-positive NSCLC has recently shifted from sequential crizotinib followed by more potent second-generation ALK TKIs to front-line second-generation TKIs. Whereas most patients derive clinical benefit from second-generation ALK TKIs, acquired resistance invariably develops and leads to clinical relapse.

Preclinical studies demonstrate that lorlatinib is more potent than earlier-generation TKIs against nonmutant ALK and retains potency against most known single ALK resistance mutations, including the highly refractory ALK G1202R solvent front mutation.

In the pivotal single arm, multicenter Phase 2 study, treatment with lorlatinib showed clinically relevant response rates and durable response in patients with ALK-positive NSCLC who had previously received at least 1 ALK TKI, including the second-generation drugs ceritinib and alectinib. In the cohort of patients previously treated with a second-generation ALK TKI (N=28), objective responses were observed in 9 patients (32%, 95% CI: 15.9-52.4). Substantial intracranial activity was also observed in these patients suffering from frequent brain metastases. The proportion of patients with objective intracranial response to lorlatinib was 55.6% (95% CI: 21.2-86.3) in patients with at least 1 measurable brain lesion at baseline (N=9). The overall and intracranial median DoR were not reached (95% CI: 4.1 months - not reached; duration of follow-up 7 months).

On the basis of pivotal Phase 1/2 Study B7461001, lorlatinib received conditional marketing authorization by the Indian Ministry of Health for the treatment of ALK fusion gene-positive unresectable advanced and/or recurrent NSCLC with resistance or intolerance to ALK TKI(s).

In view of the lack of participants in India from the Study B7461001 and of the limited number from the ongoing Phase 3 Study B7461006 (CROWN), the Indian Ministry of Health requested the Sponsor to conduct a post-approval study to obtain additional data on participants in India. The study will be conducted as a PASS.

Complete information for this compound may be found in the Single Reference Safety Document (SRSD), which for this study is the Indian product label.

## 2. STUDY OBJECTIVES AND ENDPOINTS

	Objective	Estimands		Endpoints
Pr	imary			
•	To evaluate the safety and tolerability of single-agent lorlatinib in participants with unresectable advanced and/or recurrent ALK-positive NSCLC with resistance or intolerance to at least 1 prior ALK inhibitor treatment.	• The primary estimand is the incidence of AEs from the time of first dose to at most 35 days post last dosing date or the date of initiation of a new anticancer therapy for all participants who receive at least 1 dose of lorlatinib, regardless of dosing interruptions or dosing compliance.	•	Incidence of AEs.
Se	condary			
•	To evaluate overall and intracranial antitumor activity of single-agent lorlatinib in participants with unresectable advanced and/or recurrent ALK-positive NSCLC with resistance or intolerance to at least 1 prior ALK inhibitor treatment.	• The secondary estimand is the treatment effect of lorlatinib as assessed by the investigator from time of first dose (ORR and IC-ORR) or time of first response (DoR and IC-DoR) until progression is met, death or subsequent anticancer therapy is administered for all participants who receive at least 1 dose of lorlatinib without regard to tolerability or discontinuation from treatment.	•	Confirmed ORR, confirmed IC-ORR, DoR and IC-DoR as assessed by the Investigator using RECIST version 1.1.

## **3. STUDY DESIGN**

This is a Phase 4, open-label, multicenter, non-randomized, prospective, single arm study to evaluate the safety and tolerability of lorlatinib in adult participants with unresectable advanced and/or recurrent ALK-positive NSCLC with resistance or intolerance to at least 1 prior ALK inhibitor treatment.

This study will enroll enough participants to ensure that 100 participants are treated with lorlatinib.

## 4. PARTICIPANT SELECTION

This study can fulfill its objectives only if appropriate participants are enrolled. The following eligibility criteria are designed to select participants for whom the protocol intervention is considered appropriate by their health care provider.

## 4.1. Inclusion Criteria

Participant eligibility should be reviewed and documented by an appropriate member of the Investigator's study team before participants are included in the study.

Participants must meet all of the following inclusion criteria to be eligible for enrollment into the study:

- 1. Evidence of histologically or cytologically confirmed diagnosis of unresectable advanced and/or recurrent NSCLC that carries an ALK rearrangement, as detected by an appropriate test.
- 2. Disease progression or intolerance to 1 previous treatment with ALK TKI. participants may have also had prior chemotherapy for their advanced and/or recurrent disease.
- 3. Participants with asymptomatic CNS metastases (including participants controlled with stable or decreasing steroid use within the last 2 weeks prior to study enrollment) will be eligible.
- 4. Age  $\geq 18$  years.
- 5. Eastern Cooperative Oncology Group (ECOG) performance status (PS) 0, 1, or 2.
- 6. Adequate hematologic and renal function as defined as:
  - a. Absolute neutrophil count (ANC)  $\geq 1,000/\text{mm}^3$ ;
  - b. Platelets  $\geq$  50,000/mm^3;
  - c. Hemoglobin  $\geq 8 \text{ g/dL}$ ;
  - d. Estimated creatinine clearance  $\geq$ 30 mL/min as calculated using the method standard for the institution.
- 7. Adequate liver function, including:
  - a. Total serum bilirubin  $\leq 1.5 \times$  upper limit of normal (ULN);
  - b. Aspartate aminotransferase (AST) and alanine aminotransferase (ALT)  $\leq 2.5 \times \text{ULN} (\leq 5.0 \times \text{ULN} \text{ in case of liver metastases}).$
- 8. Adequate pancreatic function, including:
  - a. Serum total amylase  $\leq 1.5 \times ULN.*$
  - b. Serum lipase  $<1.5 \times ULN$ .

\*if total amylase >1.5  $\times$  ULN, but pancreatic amylase is within the ULN, the participant may be enrolled.

- 9. Acute effects of any prior therapy resolved to baseline severity or to CTCAE Grade <1 except for AEs that in the Investigator's judgment do not constitute a safety risk for the participant.
- 10. Systemic anticancer therapy completed within a minimum of 5 half-lives of study enrollment (unless clinically meaningful tumor flare per discretion of the Investigator, in which discussion with the Sponsor is warranted).
- 11. Evidence of a personally signed and dated informed consent document indicating that the participant (or a legally acceptable representative) has been informed of all pertinent aspects of the study.
- 12. Willingness and ability to comply with the study scheduled visits, treatment plans, laboratory tests and other procedures.
- 13. Pregnancy test for females of childbearing potential negative at Screening or female participants who are not of childbearing potential (refer to Appendix 1 for definition). Male and female participants of childbearing potential and at risk for pregnancy must agree to use a highly effective method of contraception from the time of Screening, throughout the study and for 3 months after the last dose of assigned treatment, 6 months if female participants.

## 4.2. Exclusion Criteria

Participants presenting with any of the following will not be included in the study:

- Radiation therapy (except palliative to relieve bone pain) within 2 weeks of study enrollment. Palliative radiation (<10 fractions) must have been completed at least 48 hours prior to study enrollment. Stereotactic or small field brain irradiation must have completed at least 2 weeks prior to study enrollment. Whole brain radiation must have completed at least 4 weeks prior to study enrollment. Prior irradiation to >25% of the bone marrow.
- 2. Major surgery within 4 weeks prior to enrollment. Minor surgical procedures (eg, port insertion) are not excluded, but sufficient time should have passed for adequate wound healing.
- 3. Known prior or suspected severe hypersensitivity to study drug or any component in its formulation.
- 4. Active and clinically significant bacterial, fungal, or viral infection.
- 5. Clinically significant vascular (both arterial and venous) and non-vascular cardiac conditions (active or within 3 months prior to enrollment), which may include, but are not limited to:
  - a. Arterial disease such as cerebral vascular accident/stroke (including transient ischemic attack [TIA]), myocardial infarction, unstable angina;

- b. Venous diseases such as cerebral venous thrombosis, symptomatic pulmonary embolism;
- c. Non-vascular cardiac disease such as congestive heart failure (New York Heart Association Classification Class ≥II), second degree or third degree atrioventricular (AV) block (unless paced) or any AV block with PR interval >220 msec; or ongoing cardiac dysrhythmias of NCI CTCAE Grade ≥2, uncontrolled atrial fibrillation of any grade, bradycardia defined as <50 beats per minute (bpm) (unless participant is otherwise healthy such as long distance runners, etc.), machine read ECG with QT interval corrected for heart rate (QTc) >470 msec, or congenital long QT syndrome.
- 6. History or known presence of interstitial fibrosis, interstitial lung disease (ILD), pneumonitis, hypersensitivity pneumonitis, interstitial pneumonia, obliterative bronchiolitis, and pulmonary fibrosis.
- 7. Other severe acute or chronic medical or psychiatric condition, including recent (within the past year) or active suicidal ideation or behavior, or laboratory abnormality that may increase the risk associated with study participation or investigational product administration or may interfere with the interpretation of study results and, in the judgment of the Investigator, would make the participant inappropriate for enrollment in this study.
- Evidence of active malignancy (other than current NSCLC, non-melanoma skin cancer, in situ cervical cancer, papillary thyroid cancer, ductal carcinoma in situ [DCIS] of the breast or localized and presumed cured prostate cancer) within the last 3 years prior to enrollment.
- 9. Concurrent use of any of the following food or drugs (consult the Sponsor if in doubt whether a food or a drug falls into any of the categories described below) within 12 days prior to the first dose of lorlatinib:
  - a. Known strong cytochrome (CYP)3A inducers (eg, carbamazepine, enzalutamide, mitotane, rifampin, St. John's Wort).
  - b. Known strong CYP3A inhibitors (eg, grapefruit juice or grapefruit/grapefruit related citrus fruits [eg, Seville oranges, pomelos], boceprevir, cobicistat, clarithromycin, conivaptan, diltiazem, idelalisib, indinavir, itraconazole, ketoconazole, lopinavir, nelfinavir, paritaprevir, posaconazole, ritonavir alone and with elvitegravir or indinavir or lopinavir or paritaprevir or ombitasvir or dasabuvir or saquinavir or tipranavir, telaprevir and voriconazole). The topical use of these medications (if applicable), such as 2% ketoconazole cream, is allowed.
  - c. Known CYP3A substrates with narrow therapeutic index, such as pimozide, quinidine, tacrolimus, cyclosporine, sirolimus, alfentanil, fentanyl (including transdermal patch) or ergot alkaloids (ergotamine, dihydroergotamine).

- d. Known permeability glycoprotein (P-gp) substrates with a narrow therapeutic index (eg, digoxin).
- 10. Participants who are investigational site staff members directly involved in the conduct of the study and their family members, site staff members otherwise supervised by the Investigator, or participants who are Pfizer employees directly involved in the conduct of the study.
- 11. Participation in other studies involving investigational drug(s) (Phases 1-4) during study participation.
- 12. Breastfeeding female participants.

#### 4.3. Life Style Guidelines

See Appendix 1 for mandatory contraception information.

Refrain from consumption of grapefruit/grapefruit related citrus fruits (eg, Seville oranges pomelos) from 1 day before the start of study intervention until after the final dose.

Lorlatinib has moderate influence on the ability to drive and use machines. Caution should be exercised when driving or operating machinery as participants may experience CNS effects.

## **5. STUDY INTERVENTION**

Study intervention is defined as any investigational intervention(s), marketed product(s), placebo, or medical device(s) intended to be administered to a study participant according to the study protocol.

ARM name	Lorlatinib 100 mg QD
Intervention name	Lorlatinib
Туре	Small molecule
Dosage form	Tablet
Dose strength	25 mg
Dosage	100 mg QD
Route of administration	Oral
Sourcing	Provided centrally by the Sponsor
Packaging and labeling	Study intervention will be provided in bottles. Each bottle will be labeled as
	required per country requirement.
Current/former name(s) or	PF-06463922/lorlatinib
alias(es)	

## Table 1. Study Intervention(s) Administered

Abbreviation: QD=once daily.

## 5.1. Allocation to Intervention/Treatment

This is an open-label study; however, the specific intervention to be taken by a participant will be assigned using an interactive voice response system (IVRS)/interactive web response system (IWRS). The site will contact the IVRS/IWRS prior to the start of study intervention administration for each participant. The site will record the intervention assignment on the applicable case report form (CRF), if required.

# 5.2. Drug Supplies

# 5.2.1. Dosage Form(s) and Packaging

Lorlatinib (PF-06463922) will be supplied by Pfizer Global Clinical Supply for oral administration as 25 mg tablets in high-density polyethylene (HDPE) bottles with desiccant and labeled according to local regulatory requirements.

Drug supplies will be shipped to the study sites with a Drug Shipment and Proof of Receipt form. This form will be completed and filed, as directed on the bottom of the Drug Shipment and Proof of Receipt form. The Investigator shall take responsibility for and shall take all steps to maintain appropriate records and ensure appropriate supply, storage, handling, distribution, and usage of investigational product in accordance with the protocol and any applicable laws and regulations.

## 5.3. Administration

The product will be administered in accordance with the label.

The recommended dosage of lorlatinib is 100 mg orally QD, with or without food, until disease progression, unacceptable toxicity, or participant refusal/lost to follow-up. Tablets should be swallowed whole. Tablets should not be chewed, crushed, or split. Tablets should not be taken if they are broken, cracked, or otherwise not intact. Lorlatinib should be taken at the same time each day. If a dose is missed, then the missed dose should be taken unless the next dose is due within 4 hours. Two (2) doses should not be taken at the same time to make up for a missed dose. An additional dose should not be taken if vomiting occurs after lorlatinib but the next scheduled dose should be continued. Dosing interruption or dose reduction may be required based on individual safety and tolerability.

Lorlatinib dose reduction levels are summarized below:

- First dose reduction: 75 mg taken orally QD;
- Second dose reduction: 50 mg taken orally QD.

Lorlatinib should be permanently discontinued if the participant is unable to tolerate the 50 mg dose taken orally QD. Dose modification recommendations for adverse reactions are provided in Table 2.

Adverse Reaction	Lorlatinib Dosing
CNS Effect	
Grade 1	Continue lorlatinib at same dose or withhold the
	dose until recovery to baseline. Resume lorlatinib at
	the same dose or at a reduced dose.
Grade 2 or Grade 3	Withhold dose until Grade 0 or 1. Resume lorlatinib
	at a reduced dose.
Grade 4	Permanently discontinue lorlatinib.
Hyperlipidemia	
Grade 4 hypercholesterolemia or Grade 4	Withhold lorlatinib until recovery of
hypertriglyceridemia	hypercholesterolemia and/or hypertriglyceridemia to
	less than or equal to Grade 2. Resume lorlatinib at
	the same dose. If severe hypercholesterolemia
	and/or hypertriglyceridemia recurs, resume lorlatinit
	at a reduced dose.
AV block	
Second-degree AV block	Withhold lorlatinib until PR interval is less than
	200 msec. Resume lorlatinib at a reduced dose.
First occurrence of complete AV block	Withhold lorlatinib until:
	
 
pacemaker placed, or
 

	• PR interval less than 200 msec.
	If a pacemaker is placed, resume lorlatinib at the
	same dose. If no pacemaker is placed, resume
	lorlatinib at a reduced dose.
Recurrent complete AV block	Place pacemaker or permanently discontinue
	lorlatinib.
ILD/Pneumonitis	
Any grade treatment-related ILD/Pneumonitis	Permanently discontinue lorlatinib.
Other adverse reactions	
Grade 1 or Grade 2	Continue lorlatinib at same dose or reduced dose.
Grade 3 or Grade 4	Withhold lorlatinib until symptoms resolve to less
	than or equal to Grade 2 or baseline. Resume
	lorlatinib at reduced dose.

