#### 8.8. Severity Assessment

AEs will be graded by the Investigator according to the CTCAE version 4.03.

Grade	Clinical Description of Severity
1	Mild adverse event
2	Moderate adverse event
3	Severe adverse event
4	Life-threatening consequences; urgent intervention indicated
5	Death related to adverse event

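### Table 2 does not settle how Grade 3 hyperlipidemia is handled, and its recurrence trigger carries no grade, so sites can dose differently for the same lipid value

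*Protocol*

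**What the plan says.** Protocol 5.3 sends sites to one table for dose changes: "Dose modification recommendations for adverse reactions are provided in Table 2". Three pieces of text bear on lipid events.

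- **Hyperlipidemia block, Table 2.** The only entry is "Grade 4 hypercholesterolemia or Grade 4" hypertriglyceridemia. The drug is held until recovery to "less than or equal to Grade 2. Resume lorlatinib at" an unchanged level. The entry then adds a recurrence rule: "the same dose. If severe hypercholesterolemia" and/or hypertriglyceridemia comes back, treatment resumes at a lower dose. No grade is attached to that trigger.
- **Catch-all block, Table 2.** Under "Other adverse reactions", the Grade 3 or Grade 4 entry reads "Withhold lorlatinib until symptoms resolve to less" than or equal to Grade 2, or baseline, and treatment then resumes at a lower dose.
- **Protocol 8.8.** On the protocol's severity scale, Grade 3 is "Severe adverse event". Grade 4 is described as life-threatening.

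No other section says which row governs a Grade 3 lipid value. Section 5.6.2 and Appendix 2 deal with the choice of lipid-lowering agent, not with the lorlatinib dose. Section 5.3 also says that the product is given according to its label, which is not among the documents.

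**The concern.** Lipids are measured at screening and on Day 1 of every cycle (Schedule of Activities), and hyperlipidemia is one of the few reactions that Table 2 names. The eligibility criteria set no lipid limit. A Grade 3 lipid value is thus something the protocol should expect, and a site that meets one has to find its instruction in Table 2.

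Two things are at stake. The first is the participant: the same value can lead to a hold and a lower dose at one site and to no table-driven action at another. The second is the tolerability description. AE-related dose reductions and interruptions are summarized under Protocol 9.6, SAP 6.1.1.1 and SAP 6.5.3.2. To the extent that sites read the table differently, those percentages reflect the reading as well as the drug. The decisions are made during treatment, so no later analysis can undo them.

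**Working it through.** There is no plan figure to reproduce. The check is a trace of Table 2 for a participant on 100 mg QD, using the first reduction level of 75 mg QD given in Protocol 5.3.

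| Situation | Reading | What Table 2 yields |
|---|---|---|
| First event, Grade 4 | Hyperlipidemia block | Hold to Grade 2 or lower; resume at 100 mg |
| First event, Grade 3 | A: catch-all applies | Hold to Grade 2 or lower, or baseline; resume at 75 mg |
| First event, Grade 3 | B: a named reaction is not covered by the catch-all | No instruction |
| Grade 3 value after an earlier Grade 4 episode | C: *severe* has its Section 8.8 meaning | Recurrence clause triggered; resume at 75 mg |
| Grade 3 value after an earlier Grade 4 episode | D: *severe* repeats the row's own Grade 4 condition | Recurrence clause not triggered; back to A or B |

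**First event.** Under A, Grade 3 costs a dose level and Grade 4 does not. Under B, the table is silent on Grade 3. The table has a defect under either reading, so the point does not depend on choosing between them.

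**Later Grade 3 value.** The readings combine. A leads to a reduction whatever *severe* means. B with C leads to a reduction. B with D leads to no table-driven action.

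**Is the silence deliberate?** Other blocks show that the table can cover the grades in full: CNS effects have entries for Grades 1 through 4, and ILD/pneumonitis is covered at any grade. Hyperlipidemia has Grade 4 alone, with no statement about lower grades.

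**Size.** The documents give no rate of Grade 3 hyperlipidemia. Purely as an assumption, if 5% to 20% of the 100 treated participants had such a value, 0.05 × 100 = 5 to 0.20 × 100 = 20 participants would be handled differently under A and B. Their reduction and interruption percentages would then differ by at most 5 to 20 points. That ceiling requires every site to follow one reading as against every site following the other, and none of these participants to be held or reduced for another reason. It illustrates the mechanism and is not an estimate.

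**The case against.** The strongest reply is that the table can be read without conflict. Hyperlipidemia has its own heading, so on plain wording it is not among the other reactions. The catch-all also waits for symptoms to resolve, which fits a laboratory value poorly. On this view the block lists only the grade that forces a change, and lower grades are left to lipid-lowering treatment (5.6.2) and to the general allowance in 5.3 for dose changes based on individual tolerability. Likewise, *severe* has a natural meaning inside its row, namely the Grade 4 event that has just been described, and Section 8.8 does not present itself as a glossary for Table 2. The table is titled a recommendation, and the label may settle everything.

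Much of this stands. The inversion between Grades 3 and 4 is one available reading, not the only one. But the reply removes the inversion only by leaving Grade 3 without an instruction, and the table nowhere says that this is intended. The in-row meaning of *severe* is plausible, but it departs from the only severity scale in the protocol. Whether the label resolves either point cannot be checked here. If it does, Table 2 has not carried the answer over.

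Three stronger inferences are tempting and unsupported:

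- **That sites will diverge.** The text shows only that they can.
- **That 5 to 20 points of error should be set against the planned maximum standard error** of √(0.5 × 0.5 / 100) = 0.05. The rate is assumed, the shift is a ceiling, and 0.05 is a precision figure. The SAP plans no hypothesis test for the primary objective and has no decision rule (5.1.1, 5.1.2).
- **That the primary endpoint is compromised.** SAP 2.1.1 defines the variable as whether any AE occurred, regardless of dosing interruptions. Section 8.5 does make a change in dosing one reason to report an abnormal test. That could alter the indicator only for someone with no other AE and no other reporting criterion met, and nothing in the documents suggests that this would be material.

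The SAP also reports AE-related reductions and interruptions by preferred or cluster term, so lipid-driven ones would be visible. What would not be visible is which rule each site had followed.

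**Conclusion.** The concern holds as an internal inconsistency in the dosing table. Table 2 does not determine the action for Grade 3 hyperlipidemia: it is either stricter than for Grade 4 or unspecified. The recurrence trigger in the Grade 4 entry does not match the protocol's own severity scale. The consequence is possible differences between sites in dosing for the same lipid value, carried into the descriptive summaries of AE-related reductions and interruptions. The primary any-AE indicator is not affected by definition.

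The size is unknown, because no Grade 3 lipid rate is given. The conclusion rests on the protocol text alone and assumes that the label, which was not available, does not already remove the ambiguity for sites in practice. It is worth correcting because sites apply the rule prospectively and the correction is nearly free.

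**What to change.** Reconcile the Hyperlipidemia block, the catch-all block and Section 8.8 with each other and with the product label. Then:

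1. State in Table 2 which row governs each grade of hypercholesterolemia and hypertriglyceridemia, including whether the catch-all applies to lipid events.
2. Replace *severe* in the recurrence clause with the CTCAE grade that is meant.

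Which row governs, and which action follows at each grade, is for the sponsor to decide; this review takes no position on it. The cost is a clarification of one table and one communication to sites. No new procedures, data or analyses are needed.
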